## Background

Postoperative heart failure is the leading cause of extended intensive care, multiple organ failure and death after cardiac surgery(1). Conventional treatment of postoperative heart failure with inotropic drugs improves hemodynamics but at the prize of excessive increase in myocardial oxygen demand, which could aggravate the underlying myocardial injury(2).

Myocardial metabolism in patients with coronary artery disease is characterized by an increased uptake of the amino acid glutamate(3, 4). This amino acid plays a key role in the metabolism of cardiomyocytes. In animal experiments glutamate improves myocardial tolerance to ischemia\*(5, 6). After ischemia glutamate plays an important role for replenishment of Krebs cycle metabolites that have been depleted in the mitochondria and can thereby enhance normalization of the oxidative metabolism, which is disturbed after severe ischemia(7-9).

\* The suggested biochemical explanation is that glutamate can contribute to anaerobic energy production in the Krebs cycle through metabolism of  $\alpha$ -ketoglutarate to succinate, and that anaerobic glycolysis is enhanced by the malate-aspartate shuttle by maintenance of the redox potential in the cytosol. Accumulation of lactate is inhibited by transamination of pyruvate to alanine.

**STUDY PROTOCOL:** English translation - Study protocol version 5 2016-08-01 to the Swedish Medical Product Agency

A positive effect of glutamate on the metabolic and functional recovery of the heart has also been found in small studies in humans(10, 11). In light of this and encouraging clinical experience, which compare favorably with the literature both regarding survival and heart failure related complications, the first GLUTAMICS trial was initiated(12).

In this multi-center study 861 patients undergoing CABG for acute coronary syndrome were randomized to intravenous infusion of glutamate or placebo (normal saline). The primary endpoint was a composite of postoperative mortality ( $\leq 30$  days), perioperative myocardial infarction and left ventricular failure on weaning from the heart-lung machine. The results did not show any difference regarding the primary endpoint between the groups(13).

Regarding secondary endpoints significant differences were observed suggesting a beneficial effect on myocardial recovery after ischemia. Significantly fewer patients developed severe postoperative heart failure that prolonged intensive care or required treatment with intra-aortic balloon pump. The presumed effect of glutamate infusion was observed in the patients with CCS class IV angina, which constituted a prespecified subgroup. A relative risk reduction exceeding 50% was also observed in other high-risk groups (table 1) with the exception of diabetics.

A potential advantage with glutamate is that it works by enhancing normal recovery mechanisms, which should be less stressful for the heart than conventional treatment with inotropic drugs, which increase myocardial oxygen demand and thereby can aggravate underlying myocardial injury(2). Accordingly, we observed that the patients who fulfilled criteria for heart failure at weaning from the heart-lung machine had a significantly shorter ICU stay and a lower incidence of renal failure if they had received glutamate (table 2).

The first GLUTAMICS trial was originally planned for patients with unstable angina CCS class IV but the inclusion criteria were widened to include all patients with acute coronary syndrome, which resulted in inclusion of many low-risk patients which diluted the results and reduced the power of the study. We also observed that the primary endpoint would have benefited from a more robust design with regard to the criteria for heart failure due to liberal use of preemptive inotropes.

Another issue the first GLUTAMICS trial had to address was the lack of universally accepted criteria for the diagnosis of postoperative heart failure. This was done by using a blinded endpoints committee relying on prespecified criteria. Halfway into the trial NT-proBNP became available and a substudy was initiated to blindly evaluate this biomarker for heart failure against the heart failure classifications made by the endpoints committee. Our analyses demonstrated that postoperative high NT-proBNP levels were associated with postoperative heart failure (Figure 1). This implies that postoperative NT-proBNP could be used to evaluate prevention and treatment of postoperative heart failure after cardiac surgery.

The results suggest that intravenous glutamate potentially provides an important and gentle way to enhance myocardial recovery after ischemia, which also might prove useful in cardiology practice. However, the results from the first GLUTAMICS trial have received little attention due to the fact that the positive results were secondary endpoints in subgroups. For intravenous glutamate infusion to receive acceptance as treatment and prevention of heart failure after CABG the results need to be confirmed in future studies.

Our initial aim with this study was to conclusively demonstrate in a larger cohort (n=1400) that intravenous glutamate reduces the risk of severe heart failure after CABG in patients with CCS class IV angina or moderate to severe reduction of left ventricular ejection fraction (LVEF  $\leq$  0.45). Due to funding the GLUTAMICS II study has been modified and downscaled to rely on NT-proBNP as a marker of heart failure. The advantage with this redesign is that fewer patients are required and that the primary endpoint can be reproduced in future studies. Inclusion criteria have been slightly widened but the study focuses on risk patients in need of CABG. Patients accepted for CABG of at least two vessel disease with or without concomitant procedure and deemed preoperatively to carry at least a moderately increased risk for postoperative mortality (EuroSCORE II  $\geq$  3.0) will be considered for inclusion. Sample size estimations have been performed by an external professional statistician based on data from patients with EuroSCORE II  $\geq$  3.0 in the first Glutamcs-trial.

## Aims

The aim of this clinical trial is to confirm that intravenous glutamate infusion reduces the risk of postoperative heart failure in patients undergoing CABG by demonstrating mitigated increase of NT-proBNP, a biomarker for heart failure, postoperatively.

## Trial design

Externally randomized, placebo-controlled trial with parallel study groups and double-blind masking. Normal saline, which like the glutamate solution is a clear solution, will be used as placebo.

## Study population

- Patients accepted for CABG of at least two vessel disease or left main stenosis with or without a concomitant procedure and who either have:
  - EuroSCORE II  $\geq$  3.0 to which at least one of following risk factors contribute
    - LVEF  $\leq$  0.50
    - CCS-class IV
    - Myocardial infarct  $\leq$  90 days
    - Emergent or urgent procedure
    - CABG + aortic or mitral valve procedure
  - Left Ventricular Ejection Fraction  $\leq$  0.30 regardless of EuroSCORE II
- The procedure has to be done with heart-lung machine (on-pump)

These patients will be informed about the trial and asked to participate. Patients who accept participation and are operated with the aid of heart-lung machine will be included in the study.

Exclusion criteria: patients with ambiguous food allergy known to have triggered shortness of breath, rash or flushing, age >85 years, previous cardiac surgery, informed consent not possible because of critical condition, linguistic or other reason, renal failure with preoperative dialysis or calculated GFR < 30 mL/min, preoperative use of mechanical circulatory assist, surgery without heart-lung machine (off-pump), concomitant Maze-procedure for atrial fibrillation, surgery of ascending aorta, surgery of both aortic and mitral valve.

The participating centers Linköping, Örebro, Umeå, Gothenburg, Uppsala and Karlskrona are the only cardiac surgical centers within their region and thus account for all cardiac surgical procedures. To evaluate sampling bias the aim is to use the databases from each center.

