## **Research plan**

Randomized double-blind study on 310 patients fulfilling inclusion criteria. Randomization will be stratified for those undergoing isolated CABG and those undergoing CABG with concomitant procedure.

Half of the patients will receive glutamate infusion intravenously (1.65 mL/ kg bodyweight and hour of a 0.125M L-glutamic acid solution), which will be started 10-20 minutes before anticipated release of aortic cross-clamp and the start of reperfusion. The infusion will be given for 2 hours after release of aortic cross-clamp. Thereafter another 50 mL will be given with the infusion rate halved. The maximum total given will not exceed 500 mL. If the volume is insufficient due to high body weight or extension of cross-clamp time the last 50 mL should be given at half the original infusion rate. The remaining half of the patients will receive normal saline in a similar way.

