## **Specification of outcomes**

### *Primary endpoint:*

The primary endpoint is postoperative increase of NT-proBNP from the day before surgery to the third postoperative day.

.

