### **Sample size estimation and statistics**

The sample size is based on available results on NT-proBNP from the first GLUTAMICS-trial. In that study the following increase of NT-proBNP was observed in patients undergoing CABG or CABG with concomitant procedure who fulfilled inclusion criteria for the planned trial from preoperative values to postoperative day 3 (mean  $\pm$  Standard Deviation)

Glutamate (n=71):  $5261 \pm 4409$

Placebo (n=62):  $7112 \pm 6454$

Sample size estimation by statistical expertise (80% power, 5% risk level; two-sided test) suggests 141 patients in each group. To compensate for possible missed sampling and other causes for loss of data we plan to include a total of 310 patients.

Interim analysis will be performed by an independent external statistician after 160 patients in a way that does not increase the demands regarding statistical significance of the primary endpoints. An adaptive design implying that a surrogate variable (increase of NT-proBNP from preoperative level to postoperative day 1) known to correlate well with the primary endpoint will be used. Furthermore, regardless of if statistical significance is reached the study will proceed until 310 patients have been included or until the expiry date of the study solutions. Stopping criteria are given on page 12.

Continuous variables will be analyzed with a two-tailed t-test or Mann-Whitney U test depending on the distribution of data.

**STUDY PROTOCOL:** English translation - Study protocol version 5 2016-08-01 to the Swedish Medical Product Agency

Categorical variables will be analyzed with a two-tailed Chi square test unless expected cell counts are less than 5, then Fisher's exact test will be used.

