### **Clinical importance and clinical experience**

Experience from the first GLUTAMICS trial suggests that glutamate could halve the risk of developing severe postoperative heart failure and thus cardiac mortality(13). According to O'Connor postoperative heart failure was the primary cause for mortality in 2/3 of the cases in Northern New England and the single most important cause for differences between institutions with good and bad results(1).

Our group has used glutamate in clinical practice at Linköping University Hospital for 20 years and our experience so far in CABG is associated with a mortality 75% lower than expected according to EuroSCORE. Compared with national and international results we noted that the risk of renal failure (probably the most sensitive indicator for the quality of postoperative heart failure treatment) after CABG has been at least five times lower (regardless of what criteria was used)(12, 23).

Patients admitted to surgery with severely depressed left ventricular function is the group of patients that has received prophylactic treatment most frequently. In a recently published study on 104 patients, we observed a mortality of 1.0% in a cohort with an expected mortality of 8.3% according to logistic EuroSCORE(12). As this type of results are influenced by other factors, they should be interpreted cautiously but they agree with the results of the first GLUTAMICS trial.

The biochemical properties of glutamate suggest that the clinical effects we aim to confirm in the GLUTAMICS II trial should be possible to emulate in studies on other patient cohorts with acute myocardial ischemia. The major clinical implications in the future may thus be found in acute myocardial infarction and other conditions characterized by acute myocardial ischemia(18, 24).

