### **Randomization, treatment of controls, patient identification**

Randomization is planned to be done in varying block sizes by APL in Umeå, the manufacturer of the study solutions.

The infusion bottle will have two copies of the randomization code, one will be on a self-adhesive label which should be removed and transferred to the CRF when the infusion is started. This is the point when the patient is included in the trial.

Masking will be double-blind. Placebo consists of normal saline. Both the glutamate solution and placebo are clear transparent solutions implying that you cannot tell one from the other visually. The study bottles are marked with a patient code that is registered in the CRF and in the institutional data base. A patient identification list will permit identification of patients in association with data check and quality control

The randomization codes are stored at APL in Umeå. Codes can be broken for individual patients in cases of suspect adverse reactions. This decision is made after consultation with the principal investigator or his deputy.

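### Six hospitals are pooled with centre in neither the stated randomisation strata nor the primary test, so any between-centre variation in the NT-proBNP rise stays in the error term; the cost is some precision, not validity.

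*Combined protocol and SAP*

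**What the plan says.** Six hospitals take part (Study population): "The participating centers Linköping, Örebro, Umeå, Gothenburg, Uppsala and Karlskrona are the only cardiac surgical centers within their region". That section mentions centre databases only as a means of judging sampling bias.

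The only stated stratification factor is type of procedure (Research plan, and likewise the Synopsis): "Randomization will be stratified for those undergoing isolated CABG and those undergoing CABG with concomitant procedure". The section on randomisation adds that blocks vary in size and who prepares them: "Randomization is planned to be done in varying block sizes by APL in Umeå, the manufacturer of the study solutions". It does not say whether blocks are kept within a hospital.

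The primary endpoint is a continuous change (Primary endpoint): "The primary endpoint is postoperative increase of NT-proBNP from the day before surgery to the third postoperative day". The only analysis given for such variables is in Sample size estimation and statistics: "Continuous variables will be analyzed with a two-tailed t-test or Mann-Whitney U test depending on the distribution of data". No centre term, covariate or stratified test is mentioned. The only separate analysis planned is by procedure type (Subgroup analyses and substudies).

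Under Clinical importance and clinical experience, the protocol cites a regional study in which postoperative heart failure was "the single most important cause for differences between institutions with good and bad results".

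**The concern.** Hospitals can differ in case mix, surgical and anaesthetic practice, and postoperative care. If those differences affect the NT-proBNP rise, a two-group test that ignores hospital treats them as noise. The standard error is then larger than it needs to be.

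How bottles reach the hospitals decides the form this takes, and the protocol does not say. If blocks are not held within hospitals, the arms can differ by chance in their mix of hospitals, and that adds real variability to the estimate. If whole blocks go to each hospital, the arms are roughly balanced there, but the pooled test still counts hospital differences in its error and its intervals are somewhat too wide. In both cases a centre term is the natural remedy.

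At stake is precision in the one confirmatory comparison. Recruitment cannot easily be extended: the study solutions come from a single batch of 400 with a 24-month expiry, and funding is restricted (Schedule and performance). Precision that needs no extra patients is therefore worth having.

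**Working it through.** **Inputs from the documents** (Sample size estimation and statistics; Research plan)
- Mean increase: 5261 (SD 4409) on glutamate and 7112 (SD 6454) on placebo, from the first trial.
- Two-sided 5% level, 80% power, 141 per group: "Sample size estimation by statistical expertise (80% power, 5% risk level; two-sided test) suggests 141 patients in each group".
- Equal allocation: "Half of the patients will receive glutamate infusion intravenously".

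**Step 1: reproduce the plan's figure.**
- Difference = 7112 − 5261 = 1851.
- Common SD = √((4409² + 6454²)/2) = 5527.
- The t-based sample size is 140.9, so 141 per group, as stated. The normal approximation gives 140.
- Noncentral-t power at 141 per group with 280 degrees of freedom is 80.0%.

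This is the calculation for an unadjusted test, so 5527 is a total SD.

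**Step 2: standard error of the planned comparison.**
- SE = 5527 × √(2/141) = 658.

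**Step 3: add a six-level centre term.** Let ρ be the share of variance between centres. The documents do not give ρ; it is an assumption, shown as a range. With the arms balanced within centres, the adjusted SE is 658.2 × √(1 − ρ), and 5 degrees of freedom are spent (280 to 275).

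| Assumed ρ | SE | Power at 141 per group |
|---|---|---|
| 0% | 658 | 80.0% |
| 2% | 652 | 80.8% |
| 5% | 642 | 82.0% |
| 10% | 625 | 84.0% |

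At ρ = 5% the gain is worth about 0.05 × 282 = 14 analysable patients. One further degree of freedom for procedure type (274) leaves these powers unchanged to one decimal.

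**Step 4: allow for imbalance within centres.** If allocation is not blocked by hospital, fitting five centre contrasts loses on average about 5/281 = 1.8% of the information on treatment. At ρ = 0 the SE becomes 658.2/√(1 − 5/281) = 664 and power 79.3%. At ρ = 2%, 5% and 10%, power is 80.1%, 81.3% and 83.3%. In this case the term breaks even at a share of just under 2%.

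**Step 5: is the planned test valid?** A simulation with six unequal centres, 282 patients and 6000 replicates per setting gave a type I error for the unadjusted t-test of about 4% to 5.5% for ρ from 0 to 10%, with and without stratification by centre. There is no sign of excess false positives.

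**The case against.** The strongest reply is that nothing stated in the plan is wrong. The pooled test holds its level, and 141 per group is right for that test. The planning SD comes from a first trial that the Background describes as multi-centre, so it plausibly contains centre variation already, and 80% power is then not overstated on this ground. All of this stands. Step 3 uses the same reading: 5527 is the total SD, and the gain is extra precision, not a repaired shortfall.

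The gain also rests wholly on an assumed ρ. It is computed for a linear model only, whereas the plan allows a rank test, for which no gain has been worked out. This stands too.

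Four stronger readings are tempting, and the documents do not support them.
- *The protocol itself says that centre predicts the endpoint.* The sentence on institutions reports a cited regional study of mortality. The favourable mortality and renal results at the investigators' own hospital are offered as experience with glutamate, and the protocol urges caution about results of this kind. No NT-proBNP result by centre is given. The section makes centre differences plausible but does not size them.
- *Chance imbalance in hospital mix is a separate bias.* Suppose one hospital has 30% of patients and differs from the rest by half an SD. Imbalance in its share then moves the estimate with an SD of √(0.3 × 0.7 × 2/141) × 0.5 × 5527 = 151. But that scenario means 0.3 × 0.7 × 0.5² = 5.25% of variance, in effect the 5% row of the table. Taking 151 out of 658 in quadrature leaves about 641, a fall of 2.7%. It is the same small loss, already inside the standard error.
- *A positive result might rest on the lead hospital's long use of glutamate.* Allocation is external and double-blind, so local familiarity favours neither arm. With 310/6, or about 52 patients per hospital on average, results by hospital would be too imprecise to settle the question.
- *Block shipping creates a known fault.* The protocol does not say how bottles are distributed, so each branch of that argument is conditional.

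**Conclusion.** The omission is real: six hospitals are pooled, and centre is in neither the stated strata nor the primary test. The consequence is modest. At 141 per group a centre term moves power from 80.0% to between 80.0% and 84.0% for assumed between-centre shares of 0% to 10%, if the arms are balanced within hospitals. If they are not, the range is about 79.3% to 83.3%. These figures rest on the plan's own means and SDs, on a linear model, and on a variance share that the documents do not give.

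A reader might infer that the trial is underpowered, biased or at risk of a false positive on this account. None of these follows. This is an inexpensive gain in efficiency, to be taken up as an optional improvement.

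**What to change.** Before unblinding, amend Sample size estimation and statistics so that the primary comparison of the NT-proBNP increase includes centre together with procedure type, the factor already used to stratify randomisation. If means are compared, both enter a linear model as factors. If ranks are used, both act as blocking factors in a stratified (van Elteren) test. Fix in advance the rule for merging very small centres, which matters most for the rank test because crossing six centres with two procedure types gives up to 12 strata. State also whether blocks of bottles are held within hospitals.

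Results by centre may be shown, as description only.

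Cost: one or two sentences, about 5 of 280 degrees of freedom for centre and one for procedure type, and a merging rule. If centre explains nothing and allocation is not blocked by hospital, the expected loss is about 0.7 of a percentage point of power (80.0% to 79.3%). Each patient's hospital is already known, so no new data, patients or study solutions are needed, and the randomisation itself need not change.

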## **Research plan**

Randomized double-blind study on 310 patients fulfilling inclusion criteria. Randomization will be stratified for those undergoing isolated CABG and those undergoing CABG with concomitant procedure.

Half of the patients will receive glutamate infusion intravenously (1.65 mL/ kg bodyweight and hour of a 0.125M L-glutamic acid solution), which will be started 10-20 minutes before anticipated release of aortic cross-clamp and the start of reperfusion. The infusion will be given for 2 hours after release of aortic cross-clamp. Thereafter another 50 mL will be given with the infusion rate halved. The maximum total given will not exceed 500 mL. If the volume is insufficient due to high body weight or extension of cross-clamp time the last 50 mL should be given at half the original infusion rate. The remaining half of the patients will receive normal saline in a similar way.

